The study will be double-blinded as both study staff and participants will be blinded to study product allocation. Active and control product bottles will be labeled with identical product information. Each bottle will be also labeled with a randomization number assigned to a particular participant according to the appropriate allocation arm. The randomization list where randomization number and allocation code are provided will be maintained in a secure place by an independent statistician. The participants

will thus be blinded to whether they receive AA-ORS or the control solution. Study staff administering the study product and laboratory staff performing any laboratory testing will also be blinded to the product allocation.

This study will provide critical information about the safety of AA-ORS in this at-risk pediatric population and qualitative and quantitative information on the user-preferred product volume for this age group, palatability, and ease of administration. The study will also describe whether the product can be feasibly consumed for a 2-week period and if there are differences in gut health between AA-ORS and placebo groups based upon diarrhea frequency and plasma biomarkers of systemic inflammation and gut damage/repair at the end of follow-up. However, the study has not been statistically powered or designed to answer such gut health questions. Even though such exploratory comparisons will be underpowered, the baseline and follow-up biomarker data will be useful for informing study design and sample size of future EED clinical trials in this setting.

The questionnaire guides are a mix of structured and semi-structured questions. Structured questions are necessary to standardize responses to questions such as the experience with diarrheal disease treatment. Semi-structured questions allow for flexibility and richness in responses, especially those on perceptions and experiences around AA-ORS use and acceptability. Semi-structured questions are open-ended and allow for probing a participant's answers for in-depth responses. The DO checklist includes a list of questions to assess the administration of AA-ORS and explore ease of use, palatability, and acceptance of the product by the user(s).

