### *Sampling Strategy*

Estimated sample size: We expect to enroll 132 participants, which includes 66 caregivers, and 66 children (aged 12–24 months); half of these child-caregiver pairs will be randomized to receive AA-ORS (n= 33) and half to receive placebo solution (n= 33). We anticipate that there will be a dropout rate not to exceed 10%. We have incorporated this expected withdrawal rate into the final sample size numbers.

For the primary endpoint of safety in this study, 30 subjects in each arm would result in more than 95% probability of observing at least one AE if the rate of that type of event in the subject population after being exposed to AA-ORS is 10%. To have a 95% probability of being able to detect at least one AE if the rate of that event is truly 5%, the sample size would have to be at least 60 per arm. For more

rare events, the sample size would have to be much larger. Table 6 below shows the probabilities of observing an event with various sample sizes and varying true rates of that event in the population.

**Table 6.** Probability (P) of observing none, one, or more adverse events (AEs) at different true rates of AEs in the population.

N (per arm)	Rate of AE	P of 0 AEs	P of 1+ AEs	P of 2+ AEs	P of 3+ AEs
20	0.15	3.9%	96.1%	82.4%	59.5%
	0.2	1.2%	98.8%	93.1%	79.4%
30	0.1	4.2%	95.8%	81.6%	58.9%
	0.15	0.8%	99.2%	95.2%	84.9%
40	0.1	1.5%	98.5%	92.0%	77.7%
	0.15	0.2%	99.9%	98.8%	95.1%
50	0.1	0.5%	99.5%	96.6%	88.8%
	0.15	0.03%	99.97%	99.7%	98.6%
60	0.05	4.6%	95.4%	80.8%	58.3%
	0.1	0.2%	99.8%	98.6%	94.7%

Gray highlighted cells are those with a probability of 95% or higher. Blue highlighted cells are those representing a true AE rate of 0.1 or lower.

Increasing the per-arm sample size above 30 (but < 60) does not add much in terms of increasing the probability of detecting an AE with a true rate in the population of 10%. However, 30 subjects per arm has relatively low power for an efficacy endpoint using biomarkers. For example, a sample size of 30 per arm provides approximately 80% power for a t test to detect a 376 ng/ml (21.9% reduction) difference in soluble CD14 (marker of bacterial translocation) between the arms assuming the mean sCD14 is 1,715 ng/ml in the placebo group. These calculations used data from an infant cohort in Zimbabwe (23) (SD = 520 ng/ml).

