#### *Safety Monitoring*

The following procedures/evaluations will be conducted as part of the study safety assessment:

- **Medical examination** at enrollment and day 15 of follow-up: assessment of height, weight, MUAC, vital signs (i.e., temperature, pulse, respiration rate), organ systems, breathing, hydration status, fontanelles, and skin irritation/rashes.
- **Counseling procedures** that need to be adhered to during study participation.
- **Assessment of study intervention adherence** via measurement of residual solution will be performed on each bottle (numbered 1–21).
- **Assessment of adverse events** including solicited AEs (i.e., vomiting, diarrhea, fever, constipation, irritability, allergic reactions, etc.) and unsolicited AEs by study nurse initially in person, and subsequently by phone (days 4, 7, 14, 21), and review of any AEs/SAEs by study clinician.
- **Assessment of child weight** by the RA, who will weigh the child at interim visits on day 7 and 14.

To screen children for recent illness or chronic illness (e.g. HIV, hepatitis, etc.), medical charts created as part of regular medical care will be reviewed, as available. Confidentiality of medical records will be protected.

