#### *Definition of Adverse Event (AE)*

An adverse event (AE) is any untoward medical occurrence in a participant after administration of the study product and that does not necessarily have a causal relationship with the study product. An AE can therefore be any unfavorable and unintended signs (including abnormal laboratory findings), symptoms, physical examinations, or disease temporally associated with the use of the study product, whether related to the study product or not. This definition includes exacerbations of pre-existing conditions. Stable pre-existing conditions that do not change in nature or severity during the study are not considered AEs; however, these should be reported as part of the medical history.

**Solicited AEs** are pre-specified adverse events that are actively monitored by study staff during the full 21 days of follow-up. Personal communication with the study product manufacturer indicated that no adverse events have been found to be associated with the AA-ORS in adult studies or in the small study (n=5) featuring children with short bowel syndrome.

For this study, solicited AEs will be assessed by study nurse 30 minutes after the first administration (in person), and then by phone on days 4, 7, 14, and 21.

The following specific solicited adverse events will be monitored for this trial:

- *Vomiting.*
- *Diarrhea.*
- *Fever.*
- *Constipation.*
- *Lethargy.*
- *Irritability/restlessness.*
- *Allergic reactions:* sudden swelling of the face or throat, itching, and rash.
- *Other reactions:* fits (convulsions/seizures); gas, abdominal cramps, or stomach pain; weight loss.

Changes in the severity of an AE (e.g., diarrhea) will be documented to allow an assessment of the duration of the event at each level of severity to be performed. AEs characterized as intermittent require documentation of onset and duration of each episode.

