**STUDY ENDPOINTS TO BE ANALYZED AND ANALYTICAL METHODOLOGY**

**Primary:** AEs and SAEs through 21 days of follow-up, and changes to dietary and digestive habits through day 14 of follow-up.

*For AEs and SAEs that occur within 21 days of enrollment, statistical comparisons will be made between the AA-ORS and the placebo solution groups using Fisher's exact test. Changes to feeding habits (normal, less frequent/less volume, more frequent/more volume), diarrhea (1–2, 3–4, 5–7, or 7+ events in 24 hours), and vomiting (none, 1, 2–5, > 6 events in 24 hours, or hospitalization) will be made using chi-square tests.*

**Primary:** Average daily product volume consumed through 14 days of follow-up, time trends in daily volume consumed, and factors that influence children's willingness and ability to ingest the product as intended.

*The average daily volume (and statistical distribution) of solution consumed by children over the 2-week period will be calculated. These descriptive data will be pooled from AA-ORS and placebo arms as the solutions are designed to taste the same. Lowess curves will be used to describe trends in volumes consumed, and linear mixed effects models will be used to test for an association between day of follow-up and product volume consumed. We will use linear regression to identify factors (e.g., child weight, length, and age) associated with a child's average daily intake.*

**Secondary:** Key factors that influence caregivers' willingness to have the product used by their children, and their perception of their children's response to its consumption.

*These qualitative analyses will use ATLAS.ti software to identify and group key themes and topics from IDI notes.*

**Exploratory:** Average plasma/serum concentrations of metabolic, gut dysfunction, systemic inflammation, and micronutrient biomarkers at baseline and day 15 of follow-up.

*Metabolic, EED, systemic inflammation, and micronutrient marker data collected at baseline will be pooled across intervention groups and used to generate descriptive statistics for the study population. The same descriptive statistics will be generated for day 15 of follow-up. Paired student's t test will be used to compare these continuous parameters between baseline and day 15 of follow-up.*

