#### ISSUES WITH MISSING DATA AND MULTIPLICITY

We will analyze whether there is differential missingness or loss to follow-up by supplementation arm for the primary endpoints. No imputation of missing outcome data is planned. We will adjust the significance level for multiple comparisons by using the Benjamini-Hochberg method to control for the false discovery rate for related hypotheses.

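### The diarrhoea and vomiting classes in a primary safety comparison are neither exhaustive nor mutually exclusive, so it is unclear what the diarrhoea chi-square tests

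*Combined protocol and SAP*

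**What the plan says.** Section C.xi (Study endpoints to be analyzed and analytical methodology) gives the first primary endpoint two kinds of between-arm comparison.

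- For adverse events through day 21, "statistical comparisons will be made between the AA-ORS and the placebo solution groups using Fisher's exact test".
- For dietary and digestive change through day 14, chi-square tests are used. The digestive classes are "diarrhea (1–2, 3–4, 5–7, or 7+ events in 24 hours), and vomiting (none, 1, 2–5, > 6 events in 24 hours, or hospitalization".

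Other places bear on how these are read:

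- Diarrhoea and vomiting are also on the solicited list: "solicited AEs (i.e., vomiting, diarrhea, fever, constipation, irritability, allergic reactions, etc" (section C.x, Safety Monitoring). Solicited events are "pre-specified adverse events that are actively monitored by study staff during the full 21 days of follow-up" (Definition of Adverse Event).
- The data come from an interval history and stool frequency questionnaire, repeated by phone on days 4, 7, 14 and 21 (Key Activities, item 6; Interval medical history interviews).
- Study Approach and Study Population says the trial will describe "differences in gut health between AA-ORS and placebo groups based upon diarrhea frequency", then cautions that "the study has not been statistically powered or designed to answer such gut health questions".
- The case report forms are listed as Appendix 2 (section C.xiv) but are not among the documents reviewed.

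**The concern.** A contingency-table test needs each child to fall in exactly one class. The printed lists fail this in four ways:

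1. Diarrhoea starts at 1–2 events. The same sentence gives vomiting a class for none but gives diarrhoea no such class.
2. A diarrhoea count of 7 belongs to both 5–7 and 7+.
3. A vomiting count of exactly 6 belongs to neither 2–5 nor > 6.
4. Hospitalisation is an outcome, not a count. A hospitalised child who vomited three times fits two vomiting classes, and no precedence rule is given.

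In addition, the questionnaire is repeated, but the plan does not say whether the value per child is the last, the worst or a particular visit's.

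The first fault matters most. Digestive change by arm is part of the first primary objective (section C.ii), and the placebo arm is there to reveal an unusually high event rate (section C.iv). If unaffected children have no class, the diarrhoea test might compare only severity among cases. Two analysts could code the same data differently and reach different results. The coding is also needed early, because the monitoring board is to see formal interim analyses of the safety endpoint (Safety Oversight).

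**Working it through.** **The plan's own figure.** No power is stated for the diarrhoea chi-square. The nearest safety figure is in Table 6 (Sampling Strategy): the chance of at least one event with 30 children and a true rate of 10%. It reproduces: 1 − 0.9^30 = 0.958, printed as 95.8%. It concerns seeing an event in one arm, not comparing arms.

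**Inputs from the plan.** 33 per arm, or about 30 after 10% dropout (33 × 0.9 = 29.7). The 5% level is stated for the biomarkers and assumed here, before any multiplicity adjustment.

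**Assumed inputs.** The plan says only that diarrhoea may be reported at high rates (section D.i).
- Any diarrhoea, placebo vs AA-ORS: 20% vs 45%, and 20% vs 55%.
- Same severity mix in both arms. The share of cases in class 1–2 is varied, and the rest split 35:15:10 over the higher classes.

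**Method.** Multinomial counts per arm, Pearson chi-square with empty classes removed, and at least 20,000 simulated trials per scenario. Results are shown as (20% vs 45%) / (20% vs 55%).

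*Unaffected children dropped.* Number left out = 33(1 − p1) + 33(1 − p2):
- 20% vs 45%: 26.4 + 18.15 = 44.6 of 66
- 20% vs 55%: 26.4 + 14.85 = 41.3 of 66

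Power is about 4% / 5% at every share tried, which is no more than the type I error. With equal severity mixes, the remaining children carry no information on incidence.

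*Unaffected children merged into 1–2, against a five-class chi-square with a zero class:*

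| Share of cases in 1–2 | Merged | Five classes | Relative loss |
|---|---|---|---|
| 0% | 41% / 71% | 41% / 71% | none |
| 10% | 34–35% / 62% | 35% / 65% | 1–5% |
| 20% | 29% / 53% | 35% / 65% | 17–19% |
| 40% | 18% / 34% | 35% / 65% | about half |
| 70% | 6% / 11% | 37% / 67% | about 84% |

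The relative loss is 1 − merged/five-class; at 40% share, 1 − 34/65 = 48%.

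*Tests that do not depend on this coding, 33 per arm:*
- Wilcoxon rank-sum on the five ordered classes: about 57% / 83%.
- Fisher's exact test on any diarrhoea (full enumeration): 49% / 80%.

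At equal rates of 20%, the five-class chi-square rejects in about 2–3% of trials and the rank test in just under 5%. Part of the rank test's gain is therefore that the chi-square is conservative in sparse classes.

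**Sensitivity.**
- 30 per arm: dropped 4–5%; merged at 40% share 16% / 31%; Fisher 44% / 74%.
- Other rates and mix (20% vs 50%; 40/35/20/5% of cases over the four classes): merged 27% against 51% with a zero class.
- Cases more severe on AA-ORS (20/30/25/25% against 40/35/15/10%): merged 46% / 71% against 43% / 71% with five classes. Merging then costs nothing.

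**The case against.** The strongest reply is that the documents show no actual loss. Three parts of it stand.

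- **Coding.** The source is called a stool frequency questionnaire, so 1–2 may be the ordinary daily stool count. Few cases would then share that class and little or nothing would be lost. The case report form, which was not reviewed, may settle this. Even so, the analysis section calls these diarrhoea events, and a stool count still needs a place for 0.
- **Cover from Fisher's test.** Diarrhoea and vomiting are solicited adverse events, and the 21-day window contains day 14. Two passages suggest a test per event type: the sample size text refers to the chance of seeing an event "if the rate of that type of event in the subject population after being exposed to AA-ORS is 10" per cent, and the multiplicity text speaks of "using the Benjamini-Hochberg method to control for the false discovery rate for related hypotheses". A reader might infer that the trial loses its comparison of diarrhoea incidence. The documents do not support that. What is missing is a statement that Fisher's test is run for each type.
- **Power was never promised.** The plan sizes safety on seeing at least one event and disclaims power for diarrhoea frequency. Low power alone is therefore no criticism.

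It can also be said that hospitalisation is simply the top grade of a severity scale, and that counts of exactly 6 or 7 will be rare. Both are fair: these faults make coding ambiguous and cost little power. They still need a rule.

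**Conclusion.** The class faults are certain, because they can be read directly from section C.xi. They affect a first-primary comparison and should be corrected before data are analysed.

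The effect on power is conditional. It rests on assumed rates, an assumed severity mix and an unknown coding rule. On those assumptions it runs from no loss (no cases in 1–2) through about half (40% of cases there) to power no better than the type I error (unaffected children dropped). A reader might take the lower end as the expected result. The documents do not support that, since benign codings are open and greater severity on AA-ORS can remove the loss.

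The supported conclusion is narrower: as printed, the diarrhoea chi-square may not compare how many children had diarrhoea, and the plan does not say whether it does. The disclaimer about power does not cover that gap.

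**What to change.** In section C.xi:

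- Diarrhoea classes: 0, 1–2, 3–4, 5–6, 7 or more. If these are stool counts, say so, label the normal class and include 0.
- Vomiting classes: 0, 1, 2–5, 6 or more. Report hospitalisation separately.
- State the one value used per child, for example the worst through day 14.
- Compare arms on these ordered classes with a test that uses the order, such as the Wilcoxon rank-sum, instead of the nominal chi-square.
- State that Fisher's exact test is run on any diarrhoea and on any vomiting, within the Benjamini-Hochberg family.
- Check that the case report form captures the same classes.

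The cost is wording and a form check. No extra children, visits or samples are needed.

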## STUDY OVERVIEW

Title:	Safety, Acceptability, and Feasibility of enterade® in children at risk for environmental enteric dysfunction in Kakamega County, Kenya
Sponsor:	Drug Development, PATH
Investigators:	USA: [name] (co-PI), [name], [name] Kenya: [name] (co-PI), [name], [name]
Ethics committees:	Maseno University Ethics and Research Committee (MUERC) PATH Research and Ethics Committee (REC)
Regulatory authority:	Kenyan Ministry of Health (MOH) Pharmacy and Poisons Board (PPB)
Phase:	I
Study goals:	Determine the safety, acceptability, and pediatric dosing of enterade® solution, an amino acid–based oral rehydration solution (AA-ORS), for potential use in the management of environmental enteric dysfunction (EED) among children aged 12–24 months in Kenya.
Study objectives:	
 
1. Primary: To determine the safety of a 2-week course of AA-ORS among children with length-for-age Z-scores (LAZ) between –1 and –3.
 
2. Primary: To determine the feasibility and best tolerated dose of AA-ORS among children with LAZ between –3 and –1.
 
3. Secondary: To determine the perceptions among caregivers on the acceptability of AA-ORS as a potential intervention for EED.
 
4. Exploratory: To determine the impact of AA-ORS on markers of metabolism, gut dysfunction, systemic inflammation, and micronutrient status among children with LAZ between –3 and –1.
 

Study endpoints:	
 
1. Primary: Adverse events and serious adverse events through 21 days of follow-up, and changes to dietary and digestive habits through day 14 of follow-up.
 
2. Primary: Average daily product volume consumed through 14 days of follow-up, time trends in average daily volume consumed, and factors that influence children’s willingness and ability to ingest the product as intended.
 
3. Secondary: Key factors that influence caregivers’ willingness to have the product used by their children, and their perception of their children’s response to its consumption.
 
4. Exploratory: Average plasma/serum concentrations of metabolic, gut dysfunction, systemic inflammation, and micronutrient biomarkers at baseline and day 15 of follow-up.
 

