#### Objectives

**PRIMARY OBJECTIVE:** To determine the safety of AA-ORS among children with mild to moderate stunting, administered as a daily dose over 2 weeks, ad libitum up to 237 ml in 3 hours.

*Safety assessment in children will compare adverse event (AE) and serious adverse event (SAE) rates and changes to dietary and digestive habits between children receiving AA-ORS versus an inactive placebo solution containing no amino acids.*

**PRIMARY OBJECTIVE:** To determine the feasibility and well-tolerated dose of AA-ORS among children with mild to moderate growth stunting administered as a daily dose over 2 weeks, ad libitum up to 237 ml in 3 hours.

*User preferences among children include average daily volume consumed over 14 days, trends in volume consumed, and factors that influence children's willingness and ability to ingest the product as intended.*

**SECONDARY OBJECTIVE:** To determine the perceptions among caregivers on the use and acceptability of this product as a potential intervention for EED.

*Acceptability by caregivers includes factors that influence their willingness to have the product used by their children and their perception of their child's response to its consumption.*

**EXPLORATORY OBJECTIVE:** To determine the impact of AA-ORS on gut dysfunction, metabolism, gut and systemic inflammation, and micronutrient status.

*Impact of AA-ORS on gut dysfunction, systemic inflammation, and micronutrient status will be assessed by comparing non-invasive biomarker levels in blood samples collected following the intervention. These biomarkers will be assessed in both groups at baseline in order to have setting-specific descriptive data with which to power a future EED efficacy trial.*

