#### xii. Study limitations and the expected results

##### *Study Limitations*

This is an exploratory study with a small sample size that is not adequately powered for statistical comparisons of the EED outcomes (non-invasive biomarkers). As a result, the findings of this study may not be widely generalizable. This limitation will be mitigated during presentation of the study findings, which will avoid drawing conclusions beyond the scope of the study methods. The expected results from the study are intended to be useful for establishing a safety profile and reasonable pediatric dose and providing study design considerations (e.g., child EED biomarker data) for future research on the efficacy of AA-ORS and the deployment of similar EED interventions in LRS.

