Volume of solution too great.	237 ml may be too much volume for children.	Children to drink as much or as little of the solution (up to 237 ml) as desired over 3 hours. Gavage will not be done. Breastmilk will be permitted throughout this period.	Need to measure and calculate the average daily volume consumed during follow-up in order to guide dosing recommendations in future clinical trial.
Blood draw in children.	Potential discomfort, bleeding, bruising, and minimal risk of infection.	Precautions will be taken to avoid introduction of infection by disinfecting the site of venipuncture and using sterile equipment. The risk of bleeding and bruising will be minimized by immediate application of pressure after venipuncture.  Only trained, experienced phlebotomist will perform venipunctures.	Blood samples are needed in order to measure metabolic profile and biomarkers of gut dysfunction, systemic inflammation, and micronutrient status.  Metabolic profile assessment will be an important part of exploratory analysis; it is helpful to determine if the absence of certain essential amino acids leads to increase in oxidative pathways.  These biomarker measurements are important in order to have setting-specific descriptive data with which to power a future EED efficacy trial.  A comparison of these non-invasive biomarkers following the intervention will also be done.
Loss of confidentiality.	Medical information from a participant's medical record or other	Access to study records will be limited to study staff with electronic passwords (data files) or	Review of medical records will help ensure that only eligible

Potential risk to participant	Concern	Study design feature intended to minimize risk	Rationale for the necessity of exposing participants to risk
	study documents are shared inappropriately.	lock and key (physical records).  Study staff will only review medical records for eligibility assessment and will not make copies or remove such records from the hospital premises.  If the caregiver declines enrollment in the study, any medical record data collected will be discarded.	participants are enrolled in the study.  Detailed study records are critical for data analysis and reporting results accurately.

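### The tolerated-dose objective has no tolerability criterion and no analysis that joins volume drunk to adverse events

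*Combined protocol and SAP*

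**What the plan says.** The Study Overview gives the second primary objective as "To determine the feasibility and best tolerated dose of AA-ORS". The Objectives part of section C.ii words it differently: "To determine the feasibility and well-tolerated dose of AA-ORS among children with mild to moderate growth stunting". The note beneath that objective then describes it in terms of preference: "User preferences among children include average daily volume consumed over 14 days, trends in volume consumed", together with factors in willingness and ability to drink.

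There is one regimen, identical in both arms. Table 7 describes it: "Children to drink as much or as little of the solution (up to 237 ml) as desired over 3 hours".

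For this objective, the endpoints part of section C.xi plans: "The average daily volume (and statistical distribution) of solution consumed by children over the 2-week period will be calculated". It adds: "These descriptive data will be pooled from AA-ORS and placebo arms as the solutions are designed to taste the same". It also plans Lowess curves, a mixed model on day of follow-up, and a linear regression of average intake on factors that include child weight, length and age. Adverse events form the other primary endpoint and are compared between arms by Fisher's exact test.

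The populations part of C.xi assigns the volume endpoint to the per-protocol set. That set excludes early withdrawal and product discontinuation and requires a completed regimen. The safety endpoint uses everyone who received at least one dose.

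On use of the result, Table 7 says the volume measurement is to guide dosing in a future trial, and Study Limitations (C.xii) expects the results to help in "establishing a safety profile and reasonable pediatric dose".

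**The concern.** A tolerated dose is a statement about two things together: how much was taken, and what happened to the children who took it. The plan measures both but analyses them apart. For any given set of completers, the volume result is the same whether vomiting and diarrhoea cluster in the heaviest drinkers of AA-ORS or are spread evenly. The word best also implies a comparison of doses, and none is made.

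Two analysis choices widen the gap. Similar taste supports pooling with placebo for palatability, but not for tolerability of AA-ORS, because the placebo has no amino acids. And the per-protocol restriction can remove the children who did not tolerate the product from the number meant to describe tolerated intake.

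At stake is what the next trial inherits: a mean voluntary volume carrying a tolerability label that nothing in this plan tests.

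**Working it through.** **1. Is there a calculation behind the dose objective?** The sample-size section (Sampling Strategy, C.iii) sizes the study on detecting adverse events. Its figure reproduces: with 30 per arm and a true rate of 10%, the probability of at least one event is 1 − 0.9^30 = 1 − 0.0424 = 95.8%, as in Table 6. The section contains no precision target, margin or tolerability threshold for volume or dose.

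**2. Do the parts needed for a tolerated-dose conclusion exist?**
- Definition of tolerated: none found.
- Dose levels to compare: none; one cap, with self-chosen intake.
- Adverse events by volume: none; volume is not a term in the safety analysis, and adverse events are not a term in the volume analysis.
- Volume by arm: not planned; the descriptive data are pooled.
- Body weight: present as a regression factor for intake; no per-kg summary.
- Vomited product: consumption is read from bottle residuals (Interim visits, C.iii; Safety Monitoring, C.x), so a dose drunk and then vomited counts as consumed.

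**3. How do adverse events reach the volume estimate?** Only through exclusion. The discontinuation section of C.iii withdraws from product a child whose adverse event requires it, and C.xi then drops product discontinuations from the per-protocol set.

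Illustrative size, using assumed values. Let f be the fraction stopping early, m1 the completers' mean and m0 the stoppers' mean.
- All-treated mean = (1 − f)·m1 + f·m0. Per-protocol mean = m1. Difference = f·(m1 − m0).
- f = 0.05, m1 = 150, m0 = 30: 0.05 × 120 = 6 ml.
- f = 0.05, m1 = 200, m0 = 50: 0.05 × 150 = 7.5 ml.
- f = 0.10, m1 = 150, m0 = 30: 0.10 × 120 = 12 ml.
- f = 0.10, m1 = 200, m0 = 50: 0.10 × 150 = 15 ml.

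The 10% is the protocol's upper limit for dropout. The 5% and all the volumes are assumptions.

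**4. What could an analysis of events by intake show?** Take 30 children in the AA-ORS arm split at median intake (15 v 15), with a two-sided Fisher test at 0.05 and assumed event rates in the low and high halves:
- 10% v 30%: power 14.9%.
- 10% v 40%: power 32.5%.
- 10% v 50%: power 53.6%.

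Pooling both arms (30 v 30) gives 37.2%, 70.5% and 91.4%, but then half the children received no amino acids. Such a table can describe; it cannot test.

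**The case against.** The strongest reply is that this is a matter of wording. Section C.ii speaks of feasible product volume, the Study Approach text in C.iii of a user-preferred volume, and C.xi says the aim is to estimate average daily volume. The background in C.i leaves optimisation of dosing to later research, and Study Limitations promises not to conclude beyond the methods. One ad libitum presentation suits that narrower aim. This stands, and it is why the first remedy is to align the objective with those sections.

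A reader might infer that the plan ignores body weight. It does not: weight is a named factor in the regression of intake, and only a per-kg summary is missing. Spreads in ml/kg worked out at the cap from assumed weights would merely restate the ratio of those weights. Comparing amino-acid content with the quoted daily requirements would say nothing about tolerability, because a requirement is not an upper limit.

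A reader might also infer that a gastrointestinal harm of AA-ORS would go unseen. The documents do not support that. The randomised comparison by arm, the independent monitor and the DSMB all address an excess on AA-ORS. What lacks an analysis is a gradient with volume within the arm.

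Finally, intake is self-selected and ill children may drink less, so a table by intake is open to reverse causation. That also stands, and it limits what the table may claim.

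**Conclusion.** The point holds. As written, the plan can deliver the distribution of volume voluntarily drunk under one cap, its trend and its predictors. It cannot deliver a best or well-tolerated dose, because tolerability is undefined, no doses are compared, and no analysis joins volume to adverse events. Pooling with placebo and the completers-only population move the estimate further from tolerability of AA-ORS.

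It would go too far to say that the study rests on volume alone or fails its purpose. The endpoint includes trends and factors in willingness, safety is co-primary, and the narrower aim of a feasible volume is within reach. The 6–15 ml and the power figures depend on the assumed inputs shown above; the absence of a criterion and of a joint analysis does not. The change is worth making because the result is meant to inform dosing in the next trial.

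**What to change.** 1. Reword objective 2 and its conclusion as the daily volume voluntarily consumed (feasible or accepted volume, within the existing cap), consistently in the Study Overview and C.ii. Drop the best-tolerated and well-tolerated dose wording.
2. Report volume in ml/kg/day beside ml/day, by arm as well as pooled, and in all treated children as well as per protocol. State how days after stopping are counted.
3. Add a descriptive table, by arm, of solicited gastrointestinal events by prior intake in ml/kg, within the contact intervals ending on days 4, 7 and 14. Label it non-randomised and low-powered. The placebo arm serves as a check on ill children drinking less.
4. Where the adverse event record allows, flag days with vomiting. The documents do not show that vomiting at home is timed against the dose, and the case report forms in Appendix 2 were not available, so this may be possible only by day.

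Bottle residuals, weights at enrollment and on days 7 and 14, and the adverse event contacts are already planned, so no visit or sample is added. The cost is a few descriptive tables and a more modest stated claim.
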